10.3.1. Definition of AE

AE Definition

An AE is any untoward medical occurrence in a clinical study participant temporally associated with the use of study intervention, whether or not considered related to the study intervention.
 
NOTE: An AE can therefore be any unfavorable and unintended sign (including an abnormal laboratory finding), symptom, or disease (new or exacerbated) temporally associated with the use of study intervention.

Events Meeting the AE Definition

 • Any abnormal laboratory test results (hematology, clinical chemistry, or urinalysis) or other safety assessments (for example, ECG, radiological scans, vital signs measurements), including those that worsen from baseline, considered clinically significant in the medical and scientific judgment of the investigator (i.e., not related to progression of underlying disease). • Exacerbation of a chronic or intermittent pre-existing condition including either an increase in frequency and/or intensity of the condition. • New conditions detected or diagnosed after study intervention administration even though it may have been present before the start of the study. • Signs, symptoms, or the clinical sequelae of a suspected drug-drug interaction. • Signs, symptoms, or the clinical sequelae of a suspected overdose of either study intervention or a concomitant medication. Overdose per se will not be reported as an AE/SAE unless it is an intentional overdose taken with possible suicidal/self-harming intent. Such overdose should be reported regardless of sequelae.

Events NOT Meeting the AE Definition

 • Lack of drug effect is not an AE in clinical studies, because the purpose of the clinical study is to establish treatment effect. • The following study-specific clinical events related to COVID-19 are exempt from AE reporting unless the investigator deems the event to be related to the administration of intervention: 
 ○ Hypoxemia due to COVID-19 requiring supplemental oxygen; ○ Hypoxemia due to COVID-19 requiring non-invasive ventilation or high flow oxygen devices;

- Respiratory failure due to COVID-19 requiring invasive mechanical ventilation or ECMO
- Any clinically significant abnormal laboratory findings or other abnormal safety assessments which are associated with the underlying disease under study, unless judged by the investigator to be more severe than expected for the participant’s condition.
- The disease/disorder being studied or expected progression, signs, or symptoms of the disease/disorder being studied, unless more severe than expected for the participant’s condition.
- Medical or surgical procedure, such as endoscopy or appendectomy. The condition that leads to the procedure is the AE.
- Situations in which an untoward medical occurrence did not occur (social and/or convenience admission to a hospital).
- Anticipated day-to-day fluctuations of pre-existing disease(s) or condition(s) present or detected at the start of the study that do not worsen.

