10.3.2. Definition of SAE

Please note: If an event is not an AE per definition above, then it cannot be an SAE.

An SAE is defined as any AE that:
a. Results in death
b. Is immediately life-threatening The term 'life-threatening' in the definition of 'serious' refers to an event in which the participant was at risk of death at the time of the event. It does not refer to an event, which hypothetically might have caused death, if it were more severe.
c. Requires inpatient hospitalization or prolongation of existing hospitalization 
 ● In general, hospitalization signifies that the participant has been admitted to hospital for >”23 hour observation” and/or treatment that would not have been appropriate in the physician’s office or outpatient setting. Complications that occur during hospitalization are AEs. If a complication prolongs hospitalization or fulfills any other serious criteria, the event is serious. When in doubt as to whether “hospitalization” occurred or was necessary, the AE should be considered serious. ● Hospitalization for elective treatment of a pre-existing condition that did not worsen from baseline is not considered an AE.
d. Results in persistent disability/incapacity 
 ● The term disability means a substantial disruption of a person’s ability to conduct normal life functions. ● This definition is not intended to include experiences of relatively minor medical significance such as uncomplicated headache, nausea, vomiting, diarrhea, influenza,

and accidental trauma (for example, sprained ankle) which may interfere with or prevent everyday life functions but do not constitute a substantial disruption.

e. Is a congenital anomaly/birth defect

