participant	Equivalent to CDISC term "subject": an individual who participates in a clinical trial, either as recipient of an investigational medicinal product or as a control
PK	pharmacokinetics
PYAA	J2W-MC-PYAA
PYAB	J2W-MC-PYAB
PYAG	J2X-MC-PYAG
SAE	serious adverse event
SAP	statistical analysis plan
SARS-CoV-2	severe acute respiratory syndrome coronavirus 2
SC	subcutaneous(ly)
screen	The act of determining if an individual meets minimum requirements to become part of a pool of potential candidates for participation in a clinical study.
SoA	Schedule of Activities

Term	Definition
TEAE	Treatment-emergent adverse event: An untoward medical occurrence that emerges during a defined treatment period, having been absent pretreatment, or worsens relative to the pretreatment state, and does not necessarily have to have a causal relationship with this treatment.
t_{max}	time of maximum observed drug concentration
VAS	visual analog scale

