9.4 Safety and Tolerability Assessments

9.4.1 Adverse events

Where changes in severity are recorded in the Case Report Form (CRF), each separate severity of the AE will be reported in the listings, only the most severe will be used in the summary tables. A pre-existing condition is defined as an AE that starts before the subject has provided written informed consent and is ongoing at consent. A non-treatment emergent AE is defined as an AE which starts after informed consent but prior to dosing. A TEAE is defined as an AE which occurs postdose or which is present prior to dosing and becomes more severe postdose.

All AEs will be listed. All TEAEs will be summarized by treatment, severity and relationship to the study drug. The frequency (the number of AEs, the number of subjects experiencing an AE and the percentage of subjects experiencing an AE) of TEAEs will be summarized by treatment, Medical Dictionary for Regulatory Activities (MedDRA) version 23.0 system organ class and preferred term. The summary and frequency AE tables will be presented for all causalities and those considered related to the study drug by the investigator. Any SAEs will be listed.

Discontinuations due to AEs will be listed.

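### Protocol 10.3.1 makes COVID-19 hypoxemia and respiratory failure reportable as AEs only if judged related, which does not suit a healthy-participant study whose SAP tabulates AEs for all causalities

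*Protocol*

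**What the plan says.** Protocol 10.3.1, in its list of events that do not meet the AE definition, has this clause: "The following study-specific clinical events related to COVID-19 are exempt from AE reporting unless the investigator deems the event to be related". Three items follow: COVID-19 hypoxemia needing oxygen; COVID-19 hypoxemia needing non-invasive ventilation or a high-flow device; and "Respiratory failure due to COVID-19 requiring invasive mechanical ventilation or ECMO".

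The surrounding text says:

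- Protocol 10.3.1 defines an AE by its timing, "whether or not considered related to the study intervention". It also counts as AEs "New conditions detected or diagnosed after study intervention administration even though it may have been present before the start of the study".
- Protocol 10.3.2 opens with "If an event is not an AE per definition above, then it cannot be an SAE". Its hospitalization criterion nevertheless says that complications arising during a hospital stay are AEs, and that they are serious if they prolong the stay or meet another seriousness criterion.
- Protocol 10.7 says that a TEAE "does not necessarily have to have a causal relationship with this treatment".
- SAP 9.4.1 says: "The summary and frequency AE tables will be presented for all causalities and those considered related to the study drug by the investigator". Where an event changes in severity, "only the most severe will be used in the summary tables". The SAP does not mention the exemption.

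**The concern.** An exemption of this kind could make sense where COVID-19 is the disease that participants bring into the trial. Here Protocol 4.2 says that the study uses healthy people instead of COVID-19 patients, and exclusion criteria 10 and 12 in Section 5.2 remove confirmed and suspected current infection. A participant who later develops COVID-19 hypoxemia or respiratory failure would normally have a new illness, not progression of an enrolled condition.

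Whether that illness is counted then depends on a blinded investigator's causality judgment, and under Protocol 10.3.3 being unable to rule out a link is not enough for a positive one. AE, TEAE and SAE incidence is the secondary endpoint, and Protocol 4.2 gives interpretation of safety and tolerability as the reason for the placebo group. That comparison works best when events are recorded without regard to individual attribution. The situation is foreseeable: follow-up runs to Day 85, is outpatient after Day 7, and Protocol 4.1.3 already provides for home visits if a participant is infected.

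**Working it through.** The plan states no figure on this point, so the check compares the texts and follows one case through them.

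**1. What is exempt.** There are three items. The first two are the same condition at two levels of support, so they cover 3 − 1 = 2 distinct conditions: hypoxemia and respiratory failure. The only way back into AE reporting is a judgment of relatedness.

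**2. Carry-over to SAEs.** Not an AE under 10.3.1, therefore not an SAE under the opening note of 10.3.2. The hospitalization text in 10.3.2 points the other way, because ventilation or ECMO would ordinarily be given in hospital and complications there are called AEs. The two sections conflict and no rule says which prevails.

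**3. One case.** Suppose a participant is infected after discharge from the unit and is hospitalized and ventilated, and the investigator judges the complication unrelated.

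| Item | Governing text | Recorded? |
|---|---|---|
| COVID-19 diagnosis | Protocol 10.3.1 (new conditions) and 10.3.3 (prefer the diagnosis to its signs) | Probably yes; an SAE if a seriousness criterion such as hospitalization is met; summarized at worst severity under SAP 9.4.1 |
| The same diagnosis, if the disease-under-study bullet in 10.3.1 is applied | 10.3.1; Protocol 8.3.7 has no AE-recording rule to settle it | Possibly not, on a weak reading |
| Hypoxemia, either level of support | 10.3.1 exemption; 10.3.3 would usually fold it into the diagnosis anyway | Not as a separate AE |
| Respiratory failure | 10.3.1 exemption and 10.3.2 opening note, against the 10.3.2 hospitalization text | Contradictory; not recorded if the exemption is followed |

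**4. Whether other planned data show it.** Scheduled vital signs in Protocol 1.3 are blood pressure, temperature and pulse rate, with no oxygen measure. COVID-19 clinical screening in the same schedule is done at set visits and as needed. It refers to the Section 5.2 symptoms, which include hypoxia, and SAP 9.4.3 lists those data. Hypoxia may therefore appear in a listing by participant. The level of support (oxygen, ventilator, ECMO) is not among the items named.

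**5. Size per case judged unrelated.** At most 2 distinct conditions (3 listed items) go unrecorded as separate events, and fewer where hypoxemia is already part of the recorded diagnosis. Participants lost from AE or SAE incidence: 0 on the better reading, 1 only if the disease-under-study bullet is held to remove the diagnosis as well.

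**6. What does not change.** The halting criteria in Protocol 6.6.3 count related AEs only, and related events are not exempt. AUC(0-∞) and the sample size do not use AE data.

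**The case against.** The strongest reply is that this is a listed exception, labelled as study-specific, and that little is lost in practice. Section 10.3.3 asks for the diagnosis in preference to signs and symptoms, so hypoxemia would usually be absorbed into COVID-19 with or without the exemption. The hospitalization text in 10.3.2 can be read to restore the complications as AEs. Clinical screening can capture hypoxia. All of this stands and limits the point. It does not remove it: respiratory failure remains subject to two contradictory instructions, and the level of support has no other named place in the planned outputs.

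A reader might infer more than the documents support, in four ways.

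- **That the participant disappears from AE and SAE incidence.** This requires treating COVID-19 as the disease studied in people enrolled because they do not have it. That bullet also makes an exception for events more severe than expected, which respiratory failure in an overtly healthy adult of 18 to 60 plausibly is. The new-conditions text points to recording the diagnosis.
- **That the clause breaches the rule in Protocol 8.3.1 to collect all AEs and SAEs.** It narrows what counts as an AE, so there is no breach of 8.3.1 itself.
- **That it hides antibody-dependent enhancement, the theoretical risk named in Protocol 2.3.** A suspected case meets the relatedness proviso and stays reportable. Only unsuspected cases are affected.
- **That a probability or a change in incidence can be attached.** The documents give no infection or hospitalization rate, so any such number would rest on an assumed rate.

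**Conclusion.** The point holds in a limited form. The relatedness condition does not fit a healthy, infection-excluded population. It conflicts with the causality-free AE definition in its own section and with the hospitalization text in 10.3.2. If it is applied as written, a serious complication judged unrelated can be missing as a separate AE or SAE, and tables labelled as covering all causalities would not say so.

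The size is low in frequency and minor to moderate in severity. This assumes that a site follows 10.3.1 and the opening note of 10.3.2 in preference to the hospitalization text, and that the COVID-19 diagnosis is itself recorded, as is likely. The loss is then of the separate complication and its level of support, not of the participant.

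**What to change.** Delete the COVID-19 exemption and its three sub-items from Protocol 10.3.1. Add one sentence: SARS-CoV-2 infection and its complications after consent are recorded as AEs, and as SAEs when a seriousness criterion is met, regardless of causality and notwithstanding the disease-under-study bullets in the same section. Those generic bullets can otherwise stay. This reconciles 10.3.1 with 10.3.2 and 10.3.3.

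A lighter alternative is to have the SAP disclose the exemption and list these events separately by treatment. That would cure the silence in the tables, but SAP 9.1 lists only what is in the database, and a listing cannot recover an event that the protocol told the site not to record.

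The cost is a protocol amendment with IRB/IEC approval (Protocol 10.1.1) and at most a few additional AE or SAE forms. The SAP tables and the halting criteria need no change.

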10.3.2. Definition of SAE

Please note: If an event is not an AE per definition above, then it cannot be an SAE.

An SAE is defined as any AE that:
a. Results in death
b. Is immediately life-threatening The term 'life-threatening' in the definition of 'serious' refers to an event in which the participant was at risk of death at the time of the event. It does not refer to an event, which hypothetically might have caused death, if it were more severe.
c. Requires inpatient hospitalization or prolongation of existing hospitalization 
 ● In general, hospitalization signifies that the participant has been admitted to hospital for >”23 hour observation” and/or treatment that would not have been appropriate in the physician’s office or outpatient setting. Complications that occur during hospitalization are AEs. If a complication prolongs hospitalization or fulfills any other serious criteria, the event is serious. When in doubt as to whether “hospitalization” occurred or was necessary, the AE should be considered serious. ● Hospitalization for elective treatment of a pre-existing condition that did not worsen from baseline is not considered an AE.
d. Results in persistent disability/incapacity 
 ● The term disability means a substantial disruption of a person’s ability to conduct normal life functions. ● This definition is not intended to include experiences of relatively minor medical significance such as uncomplicated headache, nausea, vomiting, diarrhea, influenza,

and accidental trauma (for example, sprained ankle) which may interfere with or prevent everyday life functions but do not constitute a substantial disruption.

e. Is a congenital anomaly/birth defect


f. Other situations:
 
 • Medical or scientific judgment should be exercised in deciding whether SAE reporting is appropriate in other situations such as important medical events that may not be immediately life-threatening or result in death or hospitalization but may jeopardize the participant or may require medical or surgical intervention to prevent one of the other outcomes listed in the above definition. These events should usually be considered serious. 
 ○ Examples of such events include intensive treatment in an emergency room or at home for allergic bronchospasm, blood dyscrasias or convulsions that do not result in hospitalization, or development of drug dependency or drug abuse.

10.3.3. Recording and Follow-Up of AE and/or SAE

AE and SAE Recording

When an AE/SAE occurs, it is the responsibility of the investigator to review all documentation (for example, hospital progress notes, laboratory reports, and diagnostics reports) related to the event.
 
The investigator will then record all relevant AE/SAE information in the CRF.
 
It is not acceptable for the investigator to send photocopies of the participant’s medical records to Sponsor or designee in lieu of completion of the AE/SAE CRF page.
 
There may be instances when copies of medical records for certain cases are requested by Sponsor or designee. In this case, all participant identifiers, except the participant number, will be redacted on the copies of the medical records before submission to Sponsor or designee.
 
The investigator will attempt to establish a diagnosis of the event based on signs, symptoms, and/or other clinical information. Whenever possible, the diagnosis (not the individual signs/symptoms) will be documented as the AE/SAE.

Assessment of Intensity/Severity

The investigator will make an assessment of intensity for each AE and SAE reported during the study and assign it to one of the following categories.
 
Mild: Mild symptoms causing no or minimal interference with usual social and functional activities, with intervention not indicated.
 
Moderate: Moderate symptoms causing greater than minimal interference with usual social and functional activities, with intervention indicated.
 
Severe: Severe symptoms causing inability to perform usual social and functional activities, with intervention or hospitalization indicated.

An event is defined as ‘serious’ when it meets at least 1 of the predefined outcomes as described in the definition of an SAE, NOT when it is rated as severe.

Assessment of Causality

The investigator is obligated to assess the relationship between study intervention and each occurrence of each AE/SAE.

A “reasonable possibility” of a relationship conveys that there are facts, evidence, and/or arguments to suggest a causal relationship, rather than a relationship cannot be ruled out.

The investigator will use clinical judgment to determine the relationship.

Alternative causes, such as underlying disease(s), concomitant therapy, and other risk factors, as well as the temporal relationship of the event to study intervention administration will be considered and investigated.

The investigator will also consult the IB and/or Product Information, for marketed products, in his/her assessment.

For each AE/SAE, the investigator **must** document in the medical notes that he/she has reviewed the AE/SAE and has provided an assessment of causality.

There may be situations in which an SAE has occurred, and the investigator has minimal information to include in the initial report to Sponsor or designee. However, it is very important that the investigator always assess the causality for every event before the initial transmission of the SAE data to Sponsor or designee.

The investigator may change their opinion of causality after consideration of follow-up information and send a SAE follow-up report with the updated causality assessment.

The causality assessment is one of the criteria used when determining regulatory reporting requirements.

Follow-up of AEs and SAEs

The investigator is obligated to perform or arrange for the conduct of supplemental measurements and/or evaluations as medically indicated or as requested by Sponsor or designee to elucidate the nature and/or causality of the AE or SAE as fully as possible. This may include additional laboratory tests or investigations, histopathological examinations, or consultation with other health care professionals.

If a participant dies during participation in the study or during a recognized follow-up period, the investigator will provide the sponsor or designee with a copy of any post-mortem findings including histopathology.

New or updated information will be recorded in the originally completed CRF.

The investigator will submit any updated SAE data to Sponsor or designee within 24 hours of receipt of the information.

10.3.4. Reporting of SAEs

SAE Reporting via Paper CRF

Facsimile transmission of the SAE paper CRF is the preferred method to transmit this information to the sponsor.

Initial notification via telephone does not replace the need for the investigator to complete and sign the SAE CRF pages within the designated reporting time frames.

Contacts for SAE reporting can be found in site training documents.

10.4. Appendix 4: Contraceptive Guidance and Collection of Pregnancy Information

10.4.1. Women

Only women of non-childbearing potential may participate in this study.

Definitions:

Woman of Childbearing Potential

A woman is considered fertile following menarche and until becoming postmenopausal unless permanently sterile (see below).

If fertility is unclear (for example, amenorrhea in adolescents or athletes) and a menstrual cycle cannot be confirmed before first dose of study intervention, additional evaluation should be considered.

Woman Not of Childbearing Potential

Women in the following categories are not considered woman of childbearing potential

1. Premenarchal
2. Premenopausal female with 1 of the following:
 - Documented hysterectomy
 - Documented bilateral salpingectomy
 - Documented bilateral oophorectomy

For individuals with permanent infertility due to an alternate medical cause other than the above, (for example, mullerian agenesis, androgen insensitivity), investigator discretion should be applied to determining study entry.

Note: Documentation can come from the site personnel's: review of the participant's medical records, medical examination, or medical history interview.

3. Postmenopausal female is defined as, women with
 - 12 months of amenorrhea for women >55 years, with no need for follicle-stimulating hormone
 - 12 months of amenorrhea for women >40 years with FSH \geq 40 mIU/mL and no other medical condition such as anorexia nervosa and not taking medications during the amenorrhea (for example, oral contraceptives, hormones, gonadotropin-releasing hormone, anti-estrogens, selective estrogen receptor modulators, or chemotherapy that induced amenorrhea)

